## 9. Hypothesis

NULL hypothesis : The use of **non-surgical** treatment for three and four-parts proximal humeral fractures in elderly people (over 75 years) does not produce a statistically significant functional improvement.

MAIN hypothesis : The use of **non-surgical** treatment for three and four-parts proximal humeral fractures in elderly people (over 75 years) produces a statistically significant functional improvement.

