### *6. Objectives:*

#### 1. Main:

Evaluate the effectiveness of conservative treatment in the management of fractures in 3 and 4 fragments of the proximal humerus according to Neer classification, in patients over 75 years of age.

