### *7. Design*

Unicentric, prospective, non-randomized, open clinical trial comparing the effectiveness of the orthopaedic treatment for three and four-parts proximal humeral fractures in a patient population over 75 years of age.

Two treatments for these fractures will be compared secondarily:

1. Shoulder arthroplasty
2. Conservative treatment with sling followed by physiotherapy.

Both options are accepted today for the management in this type of fractures. [1, 2]

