### *8. Valuation variables:*

1. Main:

Efficiency measured by the use of 4 valuation scales:

a. ***THE AMERICAN SHOULDER AND ELBOW SURGEONS EVALUATION SCALE (ASES)***

*J Shoulder Elbow Surg* 1994;3:347-352.

It includes subjective information on the part of the patient and the result of a physical examination. It is possible to get a score with a maximum of 100 points, of which 50% obtain them from the subjective perception of pain and the activities of daily life.

b. ***DASHe ( Disability of Arm. Shoulder and Hand)***

*Spanish version of the DASH quartet. Med Clin ( Barc).2006;127(12):441-7*

without valuing the professional and work module.

For the final score, at least 27 of the 30 questions need to be answered. The final score is obtained by calculating the arithmetic mean of the answered questions, subtracting 1 and multiplying by 25. This calculation provides a score between 0 and 100, with the greater the disability at the highest point obtained, and considering variations with clinical significance those exceeding 10 points.

$$\left( \frac{\text{Sum of n answers}}{n} \right) - 1 \times 25$$

c. **Constant Scale**, *Clin. Orthop. Relate. Res 1987:160-4.*

It is the most used questionnaire for shoulder evaluation. It includes a subjective assessment of the pain presented by the patient, up to 15 points, the ability to perform daily activities, up to a maximum of 20 points, objective mobility assessment, up to 40 points, and strength through physical examination, up to 25. The maximum score is 100., considering results as excellent > 80, good 65-79, media 50-64, and bad <50.

d. **VAS (analog visual scale)** *Thong ISK, Jensen MP, Miró J, Tan G. The validity of pain intensity measures: what do the NRS, VAS, VRS, and FPS-R measure? Scand J Pain. 2018 Jan 26;18(1):99-107.*

It is defined as a one-dimensional scale for subjective assessment of pain by the patient. It consists of a straight line (usually 10 centimeters -100 millimeters-) at whose limits are the most extreme degrees of pain intensity, considering a score of 0 points for the lowest degree or absence of pain (usually referred to by the

patient as "painless") and 100 points for the highest degree (usually referred to as "the worst bearable" or "worst pain imaginable").

The final score (between 0 and 100 points) is obtained by measuring the distance in millimeters between the lower end (0-point score) and the mark the patient points along the line.

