## 2. Secondary:

- Comparison of the results obtained on the Constant scale with a surgical historical cohort that were treated by shoulder prostheses for this same pathology.
- Complications arising from non-surgical treatment.

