## **OBJECTIVES**

1. Main:

Compare the effectiveness of conservative treatment for the management of three and four-parts proximal humeral fractures in patients over 75 years of age.

2. Secondary:

- Compare the results obtained with a historical surgical cohort treated with shoulder prostheses for this same pathology.
- Evaluate possible complications from orthopedic treatment.

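### The only within-arm test of the main hypothesis (3 versus 12 months) cannot show that treatment produced the improvement, and the sample size serves a secondary comparison on a different scale

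*Combined protocol and SAP*

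**What the plan says.** All references are to the combined protocol and SAP.

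- **Hypothesis (section 9).** Non-surgical treatment of these fractures in "elderly people (over 75 years) produces a statistically significant functional improvement". No scale, visit, reference value or comparator is attached.
- **Main aim.** Section 6 gives it as "Evaluate the effectiveness of conservative treatment in the management of fractures in 3 and 4 fragments of the proximal humerus", and the trial title is also about evaluating one treatment. The later Objectives section words it as "Compare the effectiveness of conservative treatment for the management of three and four-parts proximal humeral fractures" and section 7 uses "comparing the effectiveness of the orthopaedic treatment". Neither phrase names what the treatment is compared with.
- **Arthroplasty comparison.** Section 7 says "Two treatments for these fractures will be compared secondarily". The secondary list in the later Objectives section has "Compare the results obtained with a historical surgical cohort treated with shoulder prostheses for this same pathology". The secondary variables in section 8 specify "Comparison of the results obtained on the Constant scale with a surgical historical cohort".
- **Main variable (section 8).** "Efficiency measured by the use of 4 valuation scales": ASES, DASH, Constant and VAS, with none put first.
- **Visits.** The follow-up schedule has sling removal at 3 weeks with no scoring, then all four scales at 3 and 12 months. Section 11 plans analysis at both times.
- **Statistical analysis.** The sample size is 20 per group for a 13-point ASES difference, with SD 15, two-sided alpha 5% and beta 20%. ASES and every other numeric variable are tested between groups. The 3- and 12-month scores are tested with a paired t or Wilcoxon test. Each p-value is judged at 0.05, and no visit is singled out.

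**The concern.** The main hypothesis is causal, but the plan gives it no test that could support a causal statement. If improvement means change within the sling group, the paired 3-versus-12-month test is the only one available, although no section assigns it to the hypothesis. Patients recovering from a fracture can be expected to score better at 12 months than at 3 months whatever the treatment. A small p-value would then be reported as effectiveness of the sling when it may be ordinary recovery.

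The one piece of design arithmetic in the plan serves something else. It sizes a two-group ASES difference, which the plan calls secondary and elsewhere places on Constant. Nothing sizes the main hypothesis. Because no scale or visit is fixed, the deciding result could also be picked after the data are seen.

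**Working it through.** **1. The plan's own figure.** Inputs from Statistical analysis: difference 13, SD 15, two-sided alpha 0.05, power 0.80.

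n per group = 2 × [15 × (1.960 + 0.842) / 13]² = 20.9

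This rounds up to 21. At 20 per group the power is 78.3% by the normal approximation and 76.1% by the t-test. The stated 20 is therefore reproduced closely enough, but only as a two-sample calculation. It belongs to the between-group ASES contrast and not to a within-arm change.

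**2. Which contrast is main.** The title, section 6 and section 9 concern one treatment. The secondary objectives in section 6, section 7, the secondary variables in section 8 and the secondary list in the later Objectives section all put arthroplasty second. The sizing paragraph is the one substantive departure.

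**3. What the paired test can detect.** n = 20 (section 10) and t(19) = 2.093. SD 15 at each visit is the plan's ASES figure. The correlation ρ between visits is assumed, because the documents give none.

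Smallest significant mean change = 2.093 × SD × √[2(1 − ρ)] / √20

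| SD | ρ = 0.3 | ρ = 0.5 | ρ = 0.7 |
|---|---|---|---|
| 10 | 5.5 | 4.7 | 3.6 |
| 15 | 8.3 | 7.0 | 5.4 |
| 20 | 11.1 | 9.4 | 7.3 |

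A change of this size is significant whatever caused it. There is no earlier score and no concurrent arm from which to subtract natural recovery.

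**4. Cost of leaving the scale open (illustration).** Chance of at least one p ≤ 0.05 when there is truly no change or difference, by simulation with multivariate normal data, 20 per group and correlations assumed:

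- Paired tests, correlation of change scores between scales 0.9 to 0.5: four scales 9.6% to 15.7%; the three functional scales (without VAS) 8.4% to 12.8%.
- Between-group tests at both visits, scale correlation 0.9 to 0.5 and visit correlation 0.7 to 0.3, cross-correlations taken as the product: four scales about 15% to 28%; three scales about 14% to 23%.

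One named test would carry 5%.

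**5. Precision if the result is an estimate.**

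- One-sample 95% half-width = 2.093 × SD / √20: 4.7, 7.0 and 9.4 points for SD 10, 15 and 20.
- Two-sample half-width, 20 per group, t(38) = 2.024: 2.024 × SD × √(2/20) = 6.4, 9.6 and 12.8 points.

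**The case against.** Several points on the other side stand.

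- A reader might infer that the plan flatly contradicts itself on its primary contrast, because one main objective says evaluate and the other says compare. The documents do not support that. The comparing phrases name no comparator and sit beside text that makes arthroplasty secondary, so they are loose wording. The justification section gives motivation and does not define a contrast.
- A reader might count 12 candidate primary tests (four scales, each between groups at two visits and once paired) and quote an error rate of 15% to 28%. That rate belongs to the between-group reading, which the text supports less well. VAS measures pain and is a weak candidate for a functional hypothesis.
- The mismatch between ASES and Constant does not leave Constant untested, since every numeric variable is compared between groups. ASES is named in both the sizing and the analysis sentence and is the implied lead scale. It is still not designated, and no visit goes with it.
- Section 7 describes the conservative treatment as a sling followed by physiotherapy, so part of the treatment may fall between 3 and 12 months. Its effect still cannot be told apart from healing.
- The study is openly non-randomized, which tempers how its claims will be read. Section 9 nevertheless states a causal hypothesis to be settled by significance.

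A 2017 start is planned, and section 8 cites a 2018 paper. A reader might infer that the main result was chosen after data were seen. A citation supporting the VAS description does not show that.

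**Conclusion.** The concern holds in two parts. First, on the best-supported, single-arm reading, the only test of improvement has no baseline and no concurrent control. It can show that scores changed between 3 and 12 months, but not that treatment caused the change. At SD 15 and 20 patients, 5.4 to 8.3 points from any cause is enough for significance, given assumed correlations of 0.7 to 0.3. Second, the sample size serves only a secondary contrast, on a scale other than the one section 8 names for it, and the main hypothesis has neither sizing nor a fixed scale and visit.

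The first part follows from the visit schedule and needs no assumption about numbers. The error rates for an open choice of scale (about 10% to 16% for four paired tests, 8% to 13% for three) are illustrations and do not carry the conclusion. The size of natural recovery is not in the documents. The sample-size arithmetic itself is not at fault.

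**What to change.** 1. Do not use the 3-to-12-month test to accept the main hypothesis. Label that change as descriptive of recovery, report it with a 95% CI, and reword section 9 without a causal verb.
2. Make the single-arm main result the 12-month score on one named functional scale with a 95% CI. ASES is the natural choice because it is the sized scale; the interval would be about ±7.0 points at n = 20 and SD 15.
3. Rest any statement relative to surgery on the historical-cohort comparison at 12 months, on one scale. Use ASES if that cohort holds it, and change the secondary variables in section 8 to match. Otherwise keep Constant and restate the detectable difference with a Constant SD. Report the difference with a 95% CI (about ±9.6 points at 20 per group and SD 15). State that the comparison is non-randomized and non-concurrent, and do not read non-significance as equivalence.
4. List the other scales and the 3-month visit as secondary. Use the same wording in section 6, section 7, section 8 (secondary variables), section 9, the later Objectives section and Statistical analysis.

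**Cost.** No extra patients or visits. It takes rewording, a check of which scales and visits the historical cohort holds, and a dated amendment. If data have already been seen, the choice must be declared post hoc. The main result becomes an estimate and no longer a significance claim, and any comparative statement stays limited by the historical control.

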## 10. Population under study and total number of patients

Number of patients: The cohort to study includes of 20 patients in which we have opted for non-surgical treatment. The historical cohort consists of 20 patients undergoing shoulder replacement.

## 11. Study calendar

The start date of the study will be the 1st and 2nd quarter of 2017.

- Recruitment of patients: 12 months
- Follow-up period (1 year per patient): 22-24 months
- Data analysis: 3 and 12 months.

## **BACKGROUND AND CURRENT STATE.**

Proximal limb fractures of the humerus are very common, representing 10% of all fractures, with an incidence of 6.6/1,000 people and year, with exponential increase from 40 years. [3-6]

Most of these fractures do not have displacement so they are successfully treated with brace immobilization and subsequent rehabilitation.

Fractures with displacement of the fragments require surgical management. We classify these fractures according to the number of fragments displaced in 1, 2, 3 and 4, according to the system proposed by Neer.

Displaced fractures type 3 and 4 of the Neer classification affecting older patients have been the subject of numerous studies with the aim of establishing the most appropriate treatment. [7,, 8]

Reconstruction with shoulder replacement, both inverted and anatomical, has been widely used as a treatment in these fractures; different studies have been launched to establish which of the two prosthetic models offers the best [1,, 9-13]. [14,, 15]

In older patients, where functional demand is not as demanding and where shoulder arthroplasty may cause various, conservative management can get a good clinical outcome in displaced fractures affecting the humeral neck. (17) [2, 15, 16]

## **JUSTIFICATION OF THE STUDY**

We know the result of surgical treatment for three and four-parts proximal humeral fractures in older patients, but it was to be established if these are superior to the results obtained with conservative treatment.

## **OBJECTIVES**

1. Main:

Compare the effectiveness of conservative treatment for the management of three and four-parts proximal humeral fractures in patients over 75 years of age.

2. Secondary:

- Compare the results obtained with a historical surgical cohort treated with shoulder prostheses for this same pathology.
- Evaluate possible complications from orthopedic treatment.

## **TYPE OF TEST AND DESIGN**

### **Selection process:**

Patients candidates for conservative treatment (three-week sling) will form the "cases" group and will be selected by the research team after their emergency care. They will be informed of the existence of this study and offered to participate in it; if they become part of the study, patients will receive orthopedic (non-surgical) treatment of their humeral fracture. Informed consent will then be given to the patient.

The "control" group will be formed by patients undergoing surgical treatment who will be selected from a historical cohort from a previous clinical trial. (FRALUX)

Patients who decline to be part of the study will receive the same treatment currently offered in our Traumatology Service, being able to manage their fracture either through surgical techniques (shoulder prostheses) or through immobilization and subsequent rehabilitation treatment. Assigning one treatment or another to each patient will depend on multiple clinical, radiological variables and the patient's own decision as has been made at the current time in our clinical practice.

### **Type of control and design**

Prospective, open, non-randomized clinical trial in a patient population over 75 years of age with three and four-parts proximal humeral fractures.

### **Follow-up period**

Each patient will have a follow-up period of one year in which they will attend:

## 1. Shoulder consultation (traumatology)

- a) At 3 weeks, sling removal and rehabilitation.
- b) 3 months ASES, CONSTANT, DASH and VAS
- c) 12 months ASES, CONSTANT, DASH and VAS

## 2. Rehabilitation consultation

- (a) At 3 weeks: rehabilitation sessions will be guidelineed.
- b) At the end of rehabilitation sessions.

## **Selection of subjects**

### **1. Inclusion criteria**

- 1. Patients over 75 years of age.
- 2. Three and four-parts proximal humeral fractures according to Neer's classification.

### **2. Exclusion Criteria**

- 1. Previous pathology that compromises functional recovery and collaboration in rehabilitative protocol (neurological pathology, cognitive impairment...)
- 2. Humerus proximal limb dislocation fractures.
- 3. Open fractures, with vascular or nerve injury.
- 4. Polytraumatized patients

## **Treatment description**

- 1. Surgical treatment. These patients have undergone shoulder surgery by implanting a reverse shoulder arthroplasty. They belong to a cohort of patients who have already

been evaluated in a previous study and who underwent this surgery because they suffered a fracture in 3 or 4 fragments according to Neer's classification.

2. Conservative treatment. It consists of the use of a sling for three weeks, which will be removed twice a day to move elbow the 1st weeks and to do Codman's pendulous exercises in the 2nd and 3rd week.

3. Concomitant treatments

Patients in the non-surgical group will undergo the same rehabilitative protocol. Physical therapy will start after evaluation made by rehabilitator physician after third week.

Patients in the surgical group also began rehabilitative treatment from the third week of surgery after their visit to the rehabilitator physician.

### **Insurance Policy**

It is considered that no insurance policy is necessary as they are two techniques that are performed in the usual surgical practice and none of them constitute a deviation from the usual clinical practice.

### **General and particular rules for researchers**

Researchers shall strictly comply with the provisions of this protocol, fully completing the data collection sheets that will be analyzed later. The study protocol will be carried out in accordance with the guidelines of current legislation, in compliance with the standards of Good Clinical Practice and the Principles set out in the Helsinki Declaration

### **Documentation file**

There will be a documentation file for all data, which will be kept in full on paper and on computer media. This file must contain the following items:

1. Approval by the CEIC of the protocol and the informed consent sheet.
2. Copy of the written consent form and protocol approved with any amendments if applicable.
3. Any correspondence with the CEIC.
4. *Curriculum vitae* of the principal investigator and the other researchers who form the research team.
5. Registration of signatures of the members of the research team.
6. List of participants' identity.
7. Copies of CRDs.

### **Terms of publication**

All information obtained during the study will be considered confidential and belong to the promoter, who undertakes to allow the researcher to publish the results and present them in scientific meetings after their consent after the study is completed and the final analysis is carried out.

## Statistical analysis

1 Sample size: Accepting an alpha risk of 5% and a beta risk of 20% in a bilateral contrast, 20 patients are required in each group to detect a difference equal to or greater than 13 units in the ASES scale score. The common standard deviation is assumed to be 15.

2 Statistical analysis: Qualitative variables shall be expressed as absolute frequencies and percentages while quantitative variables shall be presented as typical means and deviations or as medians and inter-quarterlic range depending on their normality.

Initially, the comparability of both groups will be studied to check the homogeneity of the randomization groups. Comparisons of the ASES scale and all other numeric variables between two groups will be made with student's t-test of independent measurements or Mann-Whitney test, as deemed appropriate. For repeated measurements at 3 and 12 months, the Student's t of repeated measurements or Wilcoxon test shall be used. To study the association of categorical variables, the Pearson ji-square or Fisher exact test will be used.

Differences whose p-value associated with the contrast test is less than or equal to 0.05 shall be considered significant. Data collection will be recorded in Excel database which will then be exported and analyzed in the SPSS 18 statistical program.

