#### 2. Secondary:

- Compare the results obtained with a historical surgical cohort that were treated with shoulder arthroplasty for this same pathology.
- Evaluate possible complications from orthopedic treatment.

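### The only sample-size calculation is for an ASES difference from the historical arthroplasty cohort; the plan elsewhere calls that comparison secondary and lists it on Constant, and the main hypothesis has no sample-size basis

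*Combined protocol and SAP*

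**What the plan says.** **Sample size.** Statistical analysis, item 1, states that "20 patients are required in each group to detect a difference equal to or greater than 13 units in the ASES scale score". It assumes a common SD of 15, a two-sided 5% alpha and a beta of 20%. It gives no time point. The second group can only be the 20 historical arthroplasty patients described in section 10.

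**Status and scale of that comparison.** Section 6 lists it among the secondary objectives: "Compare the results obtained with a historical surgical cohort". Section 7 says "Two treatments for these fractures will be compared secondarily". The secondary variables in section 8 put it on one scale: "Comparison of the results obtained on the Constant scale with a surgical historical cohort".

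**Main purpose.** The main objective in section 6 is non-comparative: "Evaluate the effectiveness of conservative treatment in the management of fractures". The main hypothesis in section 9 is that non-surgical treatment "produces a statistically significant functional improvement", with no comparator, scale or contrast. Other places read differently. Section 7 also describes the trial as comparing effectiveness. The Justification says of the surgical results that "it was to be established if these are superior to the results obtained with conservative treatment". The later Objectives section words the main objective as "Compare the effectiveness of conservative treatment for the management of three and four-parts proximal humeral fractures".

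**Planned tests.** Statistical analysis, item 2, plans between-group tests of ASES and of every other numeric variable. It also plans a paired test (or Wilcoxon) of the 3- and 12-month measurements. Section 8 names four main scales (ASES, DASH, Constant, VAS). The Follow-up period section schedules all four at 3 and 12 months and lists no earlier score.

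**The concern.** A power statement covers only the comparison, scale and time point for which it was computed. Here the one calculation is attached to a comparison that two sections call secondary, on a scale other than the one listed for it, at an unspecified visit. The question named as the main hypothesis has no calculation at all.

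A reader of the final report could therefore credit 80% power to the Constant comparison or to the improvement hypothesis, when the plan supports neither. With four scales and two visits, the plan also leaves open which between-group result the 13-point target refers to, and which result would answer section 9.

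**Working it through.** **1. Reproduce the stated figure.** Inputs from Statistical analysis, item 1: difference 13, SD 15, two-sided alpha 0.05, power 0.80, 20 per group.

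- Normal approximation: n = 2 × (15/13)² × (1.960 + 0.842)² = 20.9, which rounds up to 21 per group.
- Noncentral t: 21.9, which rounds up to 22 per group.

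The stated 20 is the right calculation with 20.9 not rounded up.

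**2. Power at 20 per group.**

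- Standard error of the difference: 15 × √(2/20) = 4.74.
- Normal approximation: 13/4.74 − 1.960 = 0.78, giving 78.3%.
- Noncentral t: 76.1%.

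| n per group | t-test | normal approximation |
|---|---|---|
| 20 | 76.1% | 78.3% |
| 21 | 78.2% | 80.2% |
| 22 | 80.2% | 82.0% |

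**3. Difference detectable with 80% power at 20 per group.**

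- Normal approximation: (1.960 + 0.842) × 4.74 = 13.3 points.
- t-test: 13.6 points.

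**4. Precision of the between-group difference.** The 95% half-width is t(0.975; 38) × 4.74 = 9.6 points.

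**5. What the calculation can be attached to.**

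| Place | Comparison | Scale | Time |
|---|---|---|---|
| Statistical analysis, item 1 | two groups | ASES | not stated |
| Sections 6 and 7, secondary | sling v. historical cohort | not stated | not stated |
| Section 8, secondary | sling v. historical cohort | Constant | not stated |
| Section 9 | no comparator | not stated | not stated |
| Statistical analysis, item 2, paired test | within patient | not stated | 3 v. 12 months |

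No other row matches the first on both comparison and scale. No Constant SD or target difference appears in the documents, so no power can be computed for that scale.

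**6. The section 9 hypothesis.** The documents give no target change, SD of change or within-patient correlation, so its power cannot be computed. Purely as an assumption, take 20 pairs and SD 15 at each visit. The SD of change is then 15 × √(2(1 − ρ)), and the change detectable with 80% power by a paired t-test is:

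| Assumed ρ | SD of change | Detectable change |
|---|---|---|
| 0 | 21.2 | 14.0 |
| 0.3 | 17.8 | 11.7 |
| 0.5 | 15.0 | 9.9 |
| 0.7 | 11.6 | 7.7 |

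This range, from 7.7 to 14.0 points, shows that the two-group figure does not carry over to the paired question.

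**The case against.** **The calculation belongs to a planned test.** ASES is one of the four main scales, and item 2 of the Statistical analysis tests it between groups along with all other numeric variables. The secondary objective refers to results without restricting the scale. This stands: a reader might infer that ASES was sized and then left out of the analysis, and the documents do not support that. What remains is that section 8 names a different scale for the same comparison.

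**The comparison may be the real main purpose.** Section 7, the Justification and the later Objectives section use comparative language. This stands in part, and it means the calculation cannot simply be labelled secondary. But the later Objectives section names no comparator in its main objective and still lists the historical comparison as secondary. The conflict has to be settled by the sponsor.

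**Section 9 is not without an analysis.** The paired 3-versus-12-month test is planned and is the only within-patient contrast the visit schedule allows. That also stands. What is missing is a link from section 9 to that test, a choice among the four scales, and a sample-size basis.

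**The power gap is rounding.** Agreed. One or two patients per group, or 0.3 to 0.6 ASES points of detectable difference, is small beside the uncertainty of an assumed SD. A reader might infer that the trial is materially underpowered for its stated target; the figures do not show that.

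**Equivalence.** A reader might infer that a non-significant result will be presented as showing that sling and arthroplasty are equivalent. No section states an equivalence hypothesis, margin or decision rule. Nor is the ambiguity caused by the power gap. At 20 per group, an observed difference of about 3.4 to 9.6 points would be non-significant with an interval still including 13. At 22 per group the zone would be about 3.9 to 9.1. This is a reason to report an interval, not evidence of a planned misreading.

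**Conclusion.** The concern holds as a problem of alignment. The single sample-size statement supports a between-group ASES difference from the historical cohort at an unnamed visit. It does not support the Constant comparison listed in section 8 or the hypothesis in section 9, and the documents disagree on whether the sized comparison is main or secondary.

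As a side correction, the stated beta of 20% is not quite met: power is about 76% (t-test) or 78% (normal approximation). These figures rest only on the plan's inputs of 13 points, SD 15, two-sided 5% and 20 analysed per group. No figure is claimed for Constant, and the paired range rests on assumed correlations and SD. The documents do not say which scales the historical cohort recorded, so the choice of common scale depends on that.

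**What to change.** - **Main or secondary.** Reconcile sections 6, 7 and 9, the Justification and the later Objectives section on the status of the historical comparison. State in the sample-size item that the calculation supports that comparison only.
- **Scale and time point.** Make section 8 and the sample-size item name the same scale and visit. Use ASES if the historical cohort recorded it; otherwise use Constant, with its own detectable difference from the historical SD or a stated range of SDs.
- **Section 9.** Name one scale and the contrast to be tested; 3 versus 12 months is the only within-patient contrast in the plan. Report it as an estimate with a 95% confidence interval and without claiming 80% power.
- **Between-group result.** Report the difference with its 95% confidence interval. At SD 15 and 20 per group the half-width will be about 9.6 ASES points.
- **Side correction.** Restate the power for 13 points as about 76% (t-test) or 78% (normal approximation), or give the difference detectable with 80% power as about 13.6 or 13.3 points respectively.

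**Cost.** Wording changes and a slightly less favourable stated figure; no extra patients. If Constant is kept and the historical SD cannot be obtained, only a range of detectable differences can be given.

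### Minor: the plan's own sample-size inputs call for 21 or 22 patients per group, not 20, so power at 20 per group is about 78% or 76% rather than 80%

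*Combined protocol and SAP*

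**What the plan says.** The only sample-size justification is in the combined protocol and SAP, under Statistical analysis, item 1. It sets the error rates ("Accepting an alpha risk of 5% and a beta risk of 20% in a bilateral contrast"), gives the spread ("The common standard deviation is assumed to be 15") and concludes that "20 patients are required in each group to detect a difference equal to or greater than 13 units in the ASES scale score".

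Item 2 of the same section names the test: "Comparisons of the ASES scale and all other numeric variables between two groups will be made with student's t-test of independent measurements", with Mann-Whitney as the alternative.

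Section 10 sets enrolment at the calculated figure. For the prospective arm, "The cohort to study includes of 20 patients in which we have opted for non-surgical treatment"; for the comparator, "The historical cohort consists of 20 patients undergoing shoulder replacement". Under Follow-up period, "Each patient will have a follow-up period of one year", with ASES recorded at 3 and 12 months. No allowance for loss to follow-up is stated.

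**The concern.** A required sample size is the smallest whole number that meets the stated error rates, so a fractional result is rounded up. Here the stated 20 is below what the stated inputs require, whether the normal approximation or the t-test is used. Because section 10 enrols exactly 20 per group, the error carries into the trial and the 20% beta risk is not achieved.

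What is at stake is how a non-significant between-group ASES result is read. A reader told that power was 80% would give such a result slightly more weight than it deserves. With enrolment equal to the calculated number, any missing ASES score lowers power further.

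**Working it through.** **Inputs, all from Statistical analysis, item 1:** difference 13 ASES points; common SD 15; two-sided alpha 0.05 (z = 1.960); beta 0.20 (z = 0.842); equal groups. The standardised difference is 13/15 = 0.867.

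**1. Trying to reproduce the plan's 20 (normal approximation).**

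n per group = 2 × (1.960 + 0.842)² × SD² / difference²

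= 2 × 7.849 × 225 / 169 = 20.90, which rounds up to **21**.

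The stated 20 is what results if 20.90 is truncated. A one-sided test does not explain it: that gives 17 (normal) or 18 (t-test), and the plan specifies a two-sided test.

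**2. The t-test named in the plan.** Solving the noncentral t distribution (df = 2n − 2) for 80% power gives 21.90, which rounds up to **22** per group.

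**3. Power by group size (13 points, SD 15, two-sided 5%).**

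| Patients per group | Normal approximation | Two-sample t-test |
|---|---|---|
| 20 | 78.3% | 76.1% |
| 21 | 80.2% | 78.2% |
| 22 | 82.0% | 80.2% |

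For the normal column at 20 per group: 0.867 × √(20/2) = 2.741; 2.741 − 1.960 = 0.781; Φ(0.781) = 0.783. The beta risk at 20 per group is therefore 100 − 78.3 = 21.7% (normal) or 100 − 76.1 = 23.9% (t-test), against the stated 20%.

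**4. What 20 per group would support.**

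- Difference detectable with 80% power at SD 15: normal, 15 × 2.802 × √(2/20) = 13.29 points; t-test, 13.64 points. The plan states 13.
- Largest SD at which 20 per group gives 80% power for 13 points: normal, 13 / (2.802 × √(2/20)) = 14.67; t-test, 14.30. The plan assumes 15.

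**5. One missing score.** If one sling patient has no ASES score and all 20 historical patients do (19 against 20), t-test power falls from 76.1% to 75.0%. The documents give no loss rate, so this shows only the effect of a single loss and is not a forecast.

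**The case against.** The strongest reply is that this is a rounding matter. The calculation is of the right kind, 20 lies within two patients of either answer, and by the normal approximation the shortfall is under two percentage points. That is fair as to weight, and it is why the point is graded minor.

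A second reply is that 13 and 15 may themselves be rounded. An SD of 14.67 or a difference of 13.29 would make 20 correct by the normal formula, and a pair such as 13.4 and 14.6 would give 80.7% power by t-test. This is possible, but the plan gives no sign of it. A reader can only use the figures as printed, and on those 20 is too few.

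Third, the plan does not say which formula was used, and it allows Mann-Whitney instead of the t-test, so the four-point gap depends on the method. That is true, which is why both results are shown. Neither gives 20.

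Fourth, the between-group ASES comparison is not the main objective. Section 6 makes the comparison with the surgical cohort secondary, and section 8 specifies it on the Constant scale. This is correct and limits the practical consequence. It is, however, a separate question about what the trial should be sized for, and it does not make the arithmetic right in the only sample-size statement the plan contains.

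Finally, loss can now affect only the sling arm, because the historical patients come from a completed study, and one missing score costs only about one point of power. That also stands. The absence of a loss allowance is a side remark, and the conclusion does not rest on it.

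**Conclusion.** The point holds and is minor. Taking the printed inputs as exact, 80% power needs 21 patients per group by the normal approximation or 22 by the t-test. The planned 20 gives 78.3% or 76.1%, so stated power is overstated by about 2 or 4 percentage points before any loss. The t-test figures assume normally distributed scores with equal SDs of 15 and a score for all 20 patients in each group. The shortfall does not undermine the trial, but the sentence is wrong as written.

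**What to change.** Keep enrolment as it is and replace the sample-size sentence with wording such as:

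> With 20 patients per group, a two-sample t-test at the two-sided 5% level has about 76% power to detect a between-group difference of 13 ASES points if the common SD is 15, or 80% power for a difference of 13.6 points, assuming no loss to follow-up.

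Report the number of patients with an ASES score analysed in each group beside the result.

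Restating the power is more practical than adding patients, because section 10 describes the historical cohort as 20 patients. The cost is one sentence and one count per group, and the stated power becomes slightly less favourable.
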